1.2.3 Exploratory Objectives

- Investigate repeatability of whole-body ^{68}Ga -PSMA-generator Ki Patlak imaging against that of conventional whole-body ^{68}Ga -PSMA-generator SUV imaging in patients with confirmed metastatic PCa.
- Evaluate equivalence of whole-body ^{68}Ga -PSMA Ki Patlak imaging between the two processes to create ^{68}Ga -HBED-PSMA (68GA -PSMA-cyclotron vs. 68Ga -PSMA-generator).

2. Background

2.1 Prostate Cancer

PCa is the second most lethal cancer among men in the U.S. with 26,120 estimated deaths in 2016 (1). The ability to monitor the presence and progression of prostate cancer disease sites is crucial for the approximately 400,000 American men living with advanced disease. A widely available, economically-viable imaging agent with the potential to convey predictive or prognostic multi-parametric information in the metastatic setting is a clear unmet need.

2.2 FDG Positron Emission Tomography (PET)

PET has advantages over conventional imaging methods because it quantitatively assesses biologic processes *in vivo* and can assess different processes using specific radiotracers. Processes that can be analyzed include glucose and amino acid metabolism and proliferation, blood flow, and receptor status (i.e., androgen receptor). Most studies have focused on the accumulation of FDG. FDG-PET imaging is often used in the management of advanced disease patients; however, prostate cancer is frequently not FDG-avid and the presence of avidity does not always parallel treatment efficacy. This is particularly problematic with respect to drugs in Phase II and Phase III trials. The standard RECIST criteria are difficult to apply and thus a major aim of prostate cancer research is to identify disease-specific radiotracers as an adjunct to current imaging and histologic standards, with the ultimate

goal of implementing a biomarker driven or treatment modality sensitive tracer as may be the potential for $^{68}\text{GA-PSMA}$.

2.3 Rationale- PSMA PET imaging

PSMA has been studied for several years as a target for imaging prostate cancer. An antibody targeting the intracellular portion of PSMA ($^{111}\text{In-Capromab}$) was FDA-approved in 1996 for prostate cancer imaging. Sensitivity has been found to be limited, probably due to limitations of the antibody and the SPECT imaging technology (2).

Recent clinical studies have shown that the extracellular portion of PSMA can be targeted not only by antibodies and antibody fragments, but also by urea-based small molecule inhibitors of the enzymatic activity of PSMA. Successful targeting has been shown for iodine-123 labeled probes for SPECT imaging as well as for $^{68}\text{Ga-}$ and $^{18}\text{F-labeled}$ compounds for PET imaging (3-7).

Two recent case series including 319 and 248 patients, respectively, evaluated PET/CT with $^{68}\text{Ga-HBED-PSMA}$ (PSMA PET/CT) in recurrent prostate cancer (8, 9). In these two reports the frequency of positive $^{68}\text{Ga-PSMA-generator}$ ($^{68}\text{Ga-PSMAgen}$) studies at a PSA level of less than 0.5 ng/ml was 48% (13/27) and 58% (11/19), respectively.

While $^{68}\text{Ga-PSMA}$ PET has shown utility in early clinical studies, the potential applicability will be limited by the availability and cost of the radioisotope due to its generator production. Proving equivalence with a cyclotron produced radioisotope could alleviate these constraints. Moreover, a ready source of ^{68}Ga could have implications for diseases beyond prostate cancer, where more specific PET tracers can be readily generated by the availability of cyclotron-produced ^{68}Ga .

2.4 Risk/Benefit Assessment

2.4.1 Known Potential Risks

Pharmacologic effects of HBED-PSMA

HBED-PSMA has been injected for PET imaging in more than 500 published patients. No drug related side effects have been observed. This is expected because the mass of compound is minimal, less than 10 micrograms.

Radiation exposure from PSMA PET/CT imaging

As part of this scan there is radiation delivered from the ^{68}Ga and from the low dose CT scan that are performed as part of the PET/CT for attenuation correction and co-registration. Although any exposure to ionizing radiation has the potential to cause some harm to tissue, the radiation exposures in this study are comparable to the low-level exposures associated with common diagnostic procedures such as CT scanning. There remains a low theoretical risk of developing cancer at some point later in life as a result of the radiation exposure received in this study. This risk is much smaller than the clinical risks posed by the patient's current cancer or the salvage radiation therapy the patient would be receiving. Participants should not father a baby while on this study. Acceptable birth control methods include abstinence, double barrier method, surgically sterilized patient or partner. Radiation exposure due to injection of $^{68}\text{Ga-HBED-PSMA}$ and CT imaging is provided in table 1.

Table 1: ⁶⁸Ga-PSMA 11 Patient Dosimetry (per session)

			Dose per CT Scan rad	# of Injections/CT scans
Activity of 68Ga-PSMA 11 (maximum)	3.3	mCi	0.90	1
Low dose WB CT scan	80	mA	0.90	1
Ultra-low dose WB CT scan	10	mA	0.11	3
			Total CT dose:	1.01

Target Organ	Absorbed Doses			
	rad/mCi	rad/ admininstration	rad for 4 CT scans	Total rad
Adrenals	0.0525	0.173	1.23	1.40
Brain	0.0333	0.110	1.23	1.34
Breasts	0.0326	0.107	1.23	1.34
Gallbladder Wall	0.0533	0.176	1.23	1.41
LLI Wall	0.0455	0.150	1.23	1.38
Small Intestine	0.0603	0.199	1.23	1.43
Stomach Wall	0.0444	0.147	1.23	1.38
ULI Wall	0.200	0.66	1.23	1.89
Heart Wall	0.0403	0.133	1.23	1.36
Kidneys	0.969	3.20	1.23	4.43
Liver	0.114	0.377	1.23	1.61
Lungs	0.0377	0.125	1.23	1.35
Muscle	0.0389	0.128	1.23	1.36
Pancreas	0.0511	0.168	1.23	1.40
Red Marrow	0.0340	0.112	1.23	1.34
Osteogenic Cells	0.0525	0.173	1.23	1.40
Skin	0.327	1.08	1.23	2.31
Spleen	0.165	0.54	1.23	1.77
Testes	0.0385	0.127	1.23	1.36
Thymus	0.0366	0.121	1.23	1.35
Thyroid	0.0359	0.118	1.23	1.35
Urinary Bladder Wall	0.481	1.59	1.23	2.82
Total Body	0.0459	0.151	1.23	1.38
Effective Dose (rem)	0.0873	0.288	1.23	1.52

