PI	Principal Investigator
REDCap	Research Electronic Data Capture
SAE	Serious Adverse Event
SUSAR	Suspected Unexpected Serious Adverse Reaction
UIRTSO	Unanticipated Problem Involving Risks to Subjects or Others
WCM	Weill Cornell Medicine
WCINYP	Weill Cornell Imaging NewYork Presbyterian
PCa	Prostate Adenocarcinoma
⁶⁸Ga	Gallium-68
PET	Positron Emission Tomography
ROI	Regions of Interest
PSMA	Prostate Specific Membrane Antigen
Ga-PSMAcyc	Ga-PSMA cyclotron
Ga-PSMAGen	Ga-PSMA generator

1. Protocol Summary

[figure not shown]
Full Title:	Evaluation of a ⁶⁸ Ga Small Molecule PSMA Antagonist Produced by two different Methods
Clinical Phase:	I/II
Principal Investigator:	[name]
Study Description:	Patients with metastatic prostate cancer will undergo two protocol ⁶⁸ Ga-PET scans within 24-48h with ⁶⁸ Ga-PSMA-cyclotron and ⁶⁸ Ga-PSMA-generator radiotracers. The goal of the study is to evaluate repeatability and equivalence across the different ⁶⁸ Ga-PSMA production methods.
Sample Size:	Up to 30 patients will be enrolled in the study as defined by protocol criteria.
Enrollment:	30 patients will be enrolled in this study
Study Population:	Patients with metastatic prostate adenocarcinoma
Enrollment Period:	2 years
Study Design:	Single-dose, non-randomized design. Patients with metastatic prostate adenocarcinoma will be administered a single intravenous dose of each of the study drugs ⁶⁸ Ga-PSMA-cyclotron and ⁶⁸ Ga-PSMA-generator 24-48 hours apart.
Description of Sites/ Facilities Enrolling	
Participants:	This is a single site study. All study procedures will be performed in the NYP/WCMC facilities, CBIC, and WCINYP.
Study Duration:	2 years
Participant Duration:	3 Visits: 1 screening/consent and 2-infusions imaging. The duration of patient participation can be up to 4 weeks, depending on eligibility, and the scheduling and completion of required study visits
Study Agent/Device Name	
Intervention Description:	⁶⁸ Ga-PSMA-cyclotron and ⁶⁸ Ga-PSMA-generator; single dose each, approximately 100-300 mBq.
Primary Objective:	
• To evaluate equivalence of two processes to create ⁶⁸Ga-HBED-PSMA (⁶⁸Ga-PSMA-cyclotron vs. ⁶⁸Ga-PSMA-generator)
Secondary Objectives:	
• Comparative dosimetry and biodistribution (⁶⁸Ga-PSMA-cyclotron vs. ⁶⁸Ga-PSMA-generator), whole body excretion/ metabolism in patients with confirmed metastatic PCa

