3.3 Justification for Dose

Patients will be injected with 100-300 MBq of ^{68}Ga -HBED-PSMA (from either the generator or cyclotron source) via a catheter. ^{68}Ga -PSMA PET/CT will be acquired using a Siemens Biograph mCT™ PET/CT scanner. Please see details in section 7.1.

The goal is to administer this amount of the imaging probe labeled with 2.5 MBq of ^{68}Ga per kg body weight with a minimum of 100 MBq and maximum of 300 MBq ^{68}Ga per patient.

The whole-body dynamic ^{68}Ga -PSMA scans will involve an initial dynamic scan at a pelvic scanner bed position centered over the prostate tissues for the first 10min post injection (p.i.), followed by multiple successive whole-body scans (passes) at least 10-75 min and at most 10-90 min post injection, depending on the amount of injected dosage. A fixed scan time of 30sec per bed position per pass will be used with an adjustable total number of passes. The PET data collected from at least the last six passes will be summed at each bed position and combined over all bed positions to produce whole-body static ^{68}Ga -PSMA images equivalent of a total acquisition time of $6 \times 30 \text{ sec} = 180\text{sec}$ or 3 min/bed position from all summed passes.

Due to the short physical half-life of ^{68}Ga and the decreasing elution efficiency of the $^{68}\text{Ge}/^{68}\text{Ga}$ generator during its lifetime, the amount of radioactivity injected per patient will necessarily vary. If the amount of activity per kg body weight differs by more than 25% from the recommended dose of 2.5MBq/kg of body weight, the effective total acquisition time per bed position from all passes will be adjusted by increasing the total number of passes, in increments of one pass, while keeping fixed the scan time per bed per pass. The adjustment of the total number of passes will result in the respective adjustment of the total scan time up to 90 min post injection. The total number of passes will be adjusted such that the product of total acquisition time per bed position from all summed passes participating in the synthesis of the equivalent static PET images and of the injected activity is at least 7.5 MBq/kg*min or the total scan time reached 90 min.

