7.1 Study Intervention/Patient scans

Protocol initiation quality assurance

Patient scans will be acquired on one of the Siemens Biograph mCT™ PET/CT scanners with a preference for the same instrument on all scans. Quality assurance images from each system will be acquired at the beginning of the protocol on all mCT scanners using a ^{68}Ga -filled 20-cm-diameter cylindrical water phantom with average SUVs in the range $1.0 \pm 0.5 \text{ g/ml}$ with no artifacts on visual inspection.

Individual patients preferably use the same scanner system for both scans.

Prior to imaging evaluation, patients will be permitted to eat a light meal.

An intravenous catheter (Hep-Lock) will be placed in the CBIC or WCINYP for radiopharmaceutical administration, scans, and blood sampling.

Patient scans

Two dynamic whole body ^{68}Ga -PSMA PET/CT scans will be performed successively at least 6 hours apart. As there will be an accumulation of activity in the urinary bladder, patients will have pre-treatment hydration and encourage voiding immediately prior to imaging, however the short half-life of ^{68}Ga should not result in imaging counts from the first scan to appear on the latter scan.

PET/CT imaging patients will be positioned on a flat couch in radiation treatment position. Custom-made immobilization devices, skin markings, PET/CT gantry, and room lasers will be used to ensure accurate and reproducible positioning. Imaging will start with low-dose CT scan (80 mA) for attenuation correction, followed by a PET scan. A low dose CT scan (80 mA) will be performed over the prostate or a pre-determined index lesion. A 10min dynamic PET scan at the pelvic bed position, centered over the prostate tissues, will be initiated concurrently with an intravenous bolus injection of approximately 2.5MBq/kg of body weight ($\pm 10\%$) of ^{68}Ga -PSMA, followed by a time series of whole-body PET scans (passes) at least 10-75 min and at most 10-90 min post injection. The PET acquisition time per bed position per pass will be fixed at 30sec and the total number of passes summed post acquisition to produce the static ^{68}Ga -PSMA PET images will be at least six. The total number of late passes may be increased, if needed, such that the product of total acquisition time per bed position from all passes and injected activity is at least 7.5 MBq/kg*min or a total acquisition time of 90min is reached.

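### The radiation dose table assumes a maximum of 3.3 mCi (122 MBq), but the dosing rule allows up to 300 MBq (8.11 mCi) and, at target dose, passes 122 MBq at about 49 kg

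*Combined protocol and SAP*

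**What the plan says.** Table 1 of section 2.4.1 (the dosimetry table, not the visit schedule that carries the same number) is headed "Patient Dosimetry (per session"). Its first line, labelled "Activity of 68Ga-PSMA 11 (maximum"), gives 3.3 mCi. Each organ row lists a coefficient in rad/mCi, a tracer dose per administration, a CT contribution under "rad for 4 CT scans", and a total. The text of section 2.4.1 refers the reader to this table for the exposure from injection and CT.

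The dosing text appears in three other places:

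- Section 3.3 sets a target of 2.5 MBq/kg "with a minimum of 100 MBq and maximum of 300 MBq" per patient, from either source.
- The Protocol Summary (Intervention Description) gives "single dose each, approximately 100-300 mBq". The unit is evidently MBq.
- Section 7.1 gives an "intravenous bolus injection of approximately 2.5MBq/kg of body weight", with a tolerance of 10% either way and no ceiling.

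Section 3.3 also allows for departures from target: "If the amount of activity per kg body weight differs by more than 25% from the recommended dose", whole-body passes are added until activity per kg times summed time per bed reaches 7.5 MBq/kg*min or the scan reaches 90 minutes.

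**The concern.** A dose table in a risk section should cover the largest activity the protocol permits. This one stops at 3.3 mCi and calls that the maximum, while the dosing sections permit far more and plan more for patients of ordinary adult weight. No section limits the injection to 3.3 mCi or reconciles the two ceilings.

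Participants have no direct benefit (section 2.4.2), and radiation is a main risk that the protocol describes. Table 1 is the only numerical exposure statement in the reviewed text, so the risk assessment in sections 2.4.1 and 2.4.3 should rest on the activity actually planned. Each participant has two sessions, so any shortfall occurs twice.

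**Working it through.** **Inputs.** From Table 1: 3.3 mCi; coefficients of 0.969 (kidneys), 0.481 (bladder wall) and 0.0873 (effective dose) per mCi; CT 0.90 rad for one 80 mA scan and 0.11 rad for each of three 10 mA scans. From section 3.3: 2.5 MBq/kg, minimum 100 and maximum 300 MBq. From section 7.1: tolerance of 10% either way. Conversion: 1 mCi = 37 MBq. The 60 and 80 kg body weights are assumptions for illustration.

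**Reproducing the table.** Tracer dose = coefficient × 3.3; total = tracer dose + 1.23.

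- Kidneys: 0.969 × 3.3 = 3.20; + 1.23 = 4.43 (stated 4.43).
- Bladder wall: 0.481 × 3.3 = 1.59; + 1.23 = 2.82 (stated 2.82).
- Effective dose: 0.0873 × 3.3 = 0.288; + 1.23 = 1.52 (stated 1.52).

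All 24 rows reproduce within 1%; stated tracer dose divided by coefficient runs from 3.27 to 3.32. The whole table therefore rests on 3.3 mCi, and the figure is not a stray misprint in one line.

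**Comparing the two maxima.**

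- 3.3 × 37 = 122.1 MBq.
- 300 / 37 = 8.108 mCi, and 8.108 / 3.3 = 2.46.
- Weight at which the target dose passes the table's maximum: 122.1 / 2.5 = 48.8 kg. Across the tolerance: 122.1 / 2.75 = 44.4 kg to 122.1 / 2.25 = 54.3 kg.
- Weight at which the ceiling is reached: 300 / 2.5 = 120 kg.

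**Dose per session if section 3.3 stands** (coefficient × activity in mCi + 1.23; ratio to the stated total in brackets):

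| Weight, activity | Kidneys, rad | Bladder wall, rad | Effective dose, rem | Tracer part only |
|---|---|---|---|---|
| Table 1 as stated, 3.3 mCi | 4.43 | 2.82 | 1.52 | 1 |
| 60 kg, 150 MBq, 4.054 mCi | 5.16 (1.16) | 3.18 (1.13) | 1.58 (1.04) | 1.23 |
| 80 kg, 200 MBq, 5.405 mCi | 6.47 (1.46) | 3.83 (1.36) | 1.70 (1.12) | 1.64 |
| 120 kg, 300 MBq, 8.108 mCi | 9.09 (2.05) | 5.13 (1.82) | 1.94 (1.27) | 2.46 |

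Over two sessions, the kidney shortfall is 2 × (6.47 − 4.43) = 4.08 rad at 80 kg and 2 × (9.09 − 4.43) = 9.32 rad at 300 MBq.

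**If 3.3 mCi were the real cap.** Patients above 122.1 / (2.5 × 0.90) = 54.3 kg would fall below section 7.1's tolerance. Above 122.1 / (2.5 × 0.75) = 65.1 kg, section 3.3's 25% rule would apply. An 80 kg patient would receive 122.1 / 80 = 1.53 MBq/kg, 39% below target. That patient would need 7.5 / 1.526 = 4.91 minutes per bed, which is 10 summed passes of 30 seconds against a minimum of 6.

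**CT subtotal.** One 80 mA scan and three 10 mA scans give 0.90 + 3 × 0.11 = 1.23 rad, which every organ row uses. The printed subtotal of 1.01 equals 0.90 + 0.11 and counts only one low-current scan.

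**The case against.** Five points can be made for the plan.

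- **Actual activity may fall short of target.** Section 3.3 says the injected amount will vary with the short half-life and declining generator yield, so a patient above 49 kg could still receive 122 MBq or less. This stands as a limit: 48.8 kg is the crossing point at target dose, or 44 to 54 kg across the tolerance. It does not rescue the label, because a maximum has to cover the permitted dose. Falling generator yield also does not limit the cyclotron product.
- **Low activity is provided for.** Adding passes under section 3.3 is permitted, and six is the minimum number summed, not the number acquired. Whole-body passes run for at least 65 minutes (10 to 75). Ignoring table motion, that holds 130 bed acquisitions of 30 seconds, or ten passes for up to 13 beds. The bed count is not given, so a 3.3 mCi cap need not lengthen scans. This stands. The conflict with section 7.1's tolerance above 54 kg remains.
- **The rise in effective dose is modest.** It is 4% at 60 kg, 12% at 80 kg and 27% at the ceiling, because CT dominates the total. This is correct. Nothing here shows that the comparison with common diagnostic procedures in section 2.4.1 becomes false, and the SUV comparison is untouched. The kidney and bladder wall figures change much more.
- **The CT input is itself uncertain.** Section 7.1 describes 80 mA CT at two points and never mentions the 10 mA scans. All totals above keep the table's 1.23 rad; the tracer-only ratios do not depend on it.
- **Other documents may carry other figures.** The consent form and the IND were not available, so it cannot be said which figure participants or regulators were given.

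**Conclusion.** The concern holds. Table 1's stated maximum is below what the protocol's own dosing rule gives to a patient above about 49 kg dosed at target. If the 300 MBq ceiling stands, the tracer component is understated by up to 2.46-fold. Per session at that ceiling, the kidney total is 9.09 rather than 4.43 rad, the bladder wall total 5.13 rather than 2.82 rad, and effective dose 1.94 rather than 1.52 rem.

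These figures rest on the table's own coefficients, its 1.23 rad CT dose, and dosing at 2.5 MBq/kg. Which maximum the sponsor intended cannot be settled from the documents, but the text needs correcting on either reading. The multiplication within the organ rows is sound. The fault is the activity they start from, plus one wrong CT subtotal that changes no row.

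**What to change.** Decide which maximum governs, then make every section agree.

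- **If 300 MBq:** recompute all rows of Table 1 as coefficient × 8.108 mCi plus CT, relabel the activity line 8.11 mCi, and revise the risk text in section 2.4.1 to match. The cost is one table and a paragraph.
- **If 3.3 mCi:** replace the 300 MBq ceiling and the 2.5 MBq/kg rule in section 3.3, the 100 to 300 range in the synopsis and the weight-based dose in section 7.1. Then check, with the actual number of bed positions, that enough passes can be summed to reach 7.5 MBq/kg*min. The cost is dosing text in three places and possibly more passes.

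In either case, correct the CT subtotal from 1.01 to 1.23 rad. State in section 7.1 how many CT scans are done at each current, so that it matches the one 80 mA and three 10 mA scans in Table 1. If the CT count changes, update the totals. Correct the unit in the synopsis to MBq.

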2.4.2 Known Potential Benefits

This is not a therapeutic study and no direct benefit exists for the participants.

2.4.3 Assessment of Potential Risks and Benefits

This study will be the basis of expanding access by enabling greater production of gallium. It will also enable our investigative team to look at the value of the information that we get from the Ga-PSMA PET scans that they may continue to have after the results of this study are documented and published.

The amount of extra radiation exposure in these scans will not significantly impact the patients in a way that has been discovered in any systematic study of PET scanning.

2.5 Correlative Studies Background- Preliminary laboratory and small animal experience

The PSMA ligand is a zinc metalloenzyme carboxypeptidase that catalyzes the hydrolysis of glutamate from the C terminus of peptides. The antagonist ^{68}Ga -HBED-PSMA targets this ligand and will be produced using the following methods.

2.5.1 Generator Production

^{68}Ga -gallium chloride is generated from an IGG100 Eckert and Ziegler closed system ^{68}Ga - generator consisting of a borosilicate glass column containing a titanium dioxide bed on which ^{68}Ge is absorbed and fully shielded. This study will therefore be performed under the specifications set forth by **IND 124495**. Both, the HBED-PSMA non-radioactive precursor and the ^{68}Ga radionuclide will be obtained from the **CBIC core** and accompanied by a certificate of analysis as described in the Chemistry, Manufacturing, and Controls (CMC) Section of the IND. A single dose will be delivered to the CBIC scanner or WCINYP with 2 h expiration.

2.5.2 Cyclotron Production

[figure not shown]
Gallium-68 will be produced by **NCM USA LLC**, a NYC-based advanced PET radiopharmaceutical manufacturing and distribution company ([name]) with whom we have an academic-industrial partnership NIH grant to investigate manufacturing this nuclide based on an IND held by the company. In summary, the NCM cyclotron will use enriched (>99% purity) zinc-68 target, the target will first be dissolved in 10-12 N HCl and solution will be passed on AG-50W-X8 resin to separate Zn-68 and elute gallium Gallium-68 as ^{68}Ga - GaCl_3 in 3N HCl. The cyclotron produced ^{68}Ga that will be released by NCM for labeling and formulation of the ^{68}Ga -HBED-PSMA product. The radiochemical purity of the in house product will be required to match and be equivalent to the specifications of the ^{68}Ga -HBED-PSMA generator produced radiopharmaceutical.

2.5.2.1 Purity of cyclotron-produced ^{68}Ga (HPLC)

[figure not shown]
We measured radionuclide purity and identity using an ORTEC GEM series HPGe (high-purity Germanium) coaxial detector system (model GEM20-70-SMP, CFG-SV-70). The purified sample of ^{68}Ga showed only two peaks at 511 keV and 1077 keV.

